5.2.1.4 We will first treat 6 patients at dose level -1 in the lead-in phase. If DLT occurs in $\geq 2/6$ patients, this dose level would exceed the MTD, and 6 patients will be treated at the next lower dose level (i.e. dose level -2). If DLT is observed in the first 28 days of treatment in 0 or 1/6 at dose level -1, then dose level 0 will be evaluated. The dose adjustment (Table 1) will continue in cohorts of 6 until we reach a dose level at which $< 2/6$ patients experience a DLT in the first 28 days. The dose level at which 0-1/6 patients experience a DLT in the first 28 days of treatment will be the MTD and will be used to treat an additional 34 patients in the phase II portion of the study. If $\geq 2/6$ patients experience DLT at dose level -4, the study will be revised to consider additional lower dose levels (based on potential synergistic toxicity).

5.2.1.5 Patients that are removed from study before day 28 for any reason other than toxicity and have not experienced DLT will be replaced.

5.2.2 One cycle of therapy is defined as 28 days. Patients will receive one cycle of therapy every 28 days (+/- 7 days).

5.2.2.1 In the phase II part of the study (once the MTD dose has been defined) cycles may be started early (but not earlier than day 21) for patients with active disease if judged in the best interest of the patient.

For the lead-in cohort, DLT defining period is 28 days. As such, cycle 2 should not be started before 28 days for the patients being treated on the lead-in cohort.

5.2.2.2 Subsequent cycles may be delayed for recovery of toxicity or other medical conditions (e.g. infections). Delays in start of subsequent cycles greater than 8 weeks will be acceptable only for patients who are deriving clinical benefit and after discussion with the principal investigator of potential risk/benefit ratio.

5.2.2.3 In instances where one drug has to be discontinued transiently because of safety, the administration of the other drug may continue as scheduled. If the drug that is held can resume at a later time, no doses will be made up and the administration will follow the originally defined schedule calendar according to the drug that was continued.

5.2.2.4 Subsequent courses of 5-azacytidine and lirilumab may be administered regardless of peripheral blood counts during the first 4 cycles and/or in the presence of residual leukemia.

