11.1 Sample Size

Part a. Lead-in phase

The primary objective of the lead-in phase is to determine the safety of lirilumab in combination with 5-azacytidine in patients with refractory/ relapsed AML. Up to 24 patients will be accrued into lead-in part of the study.

Part b. Phase II

Up to 40 patients (including 6 patients treated at the MTD from the lead-in part) will be recruited for the Phase II part.

The primary objective of the phase II is to determine the efficacy of lirilumab in combination with 5-azacytidine in patients with refractory, relapsed or untreated AML. The efficacy of the combination will be measured by the overall response rate (ORR), defined as CR (complete remission) + CRp (complete remission with incomplete platelet recovery) + CRi (complete remission with incomplete count recovery) + PR (partial response) + marrow clearance of blasts + HI (Hematological improvement) within 3 months of treatment initiation among adult patients with refractory/ relapsed AML. ORR and toxicity will be monitored simultaneously using the Bayesian approach of Thall, Simon, Estey (1995, 1996) and the extension by Thall and Sung (1998).

Once safety of the MTD has been established, any patients still on study at a dose lower than MTD can be dose escalated up to MTD. Patients treated in the lead-in phase at MTD will be included in the phase II portion of the study.

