11.2 Statistical Design

Part a. Lead-in phase

The MTD is defined as the highest dose level with ≤ 1 out of 6 patients experience a DLT during the first 28 days of treatment. DLT is defined in section 5.2.2. The dosing schema for the combination treatment during the lead in phase is shown in Table 1 in section 5.2.1.

Part b. Phase II

Historical data on similar patients shows an ORR of 10-15%. The target ORR with the experimental treatment is 30%. This regimen of the combination treatment will be considered worthy of further investigation if it elicits an increase in ORR to 30% with acceptable toxicity. A $>30\%$ drug-related grade 3/4 toxicity rate is considered unacceptable. Thus, interim monitoring rules, assuming the prior distributions above, were constructed that meet the following two conditions,

- 1) Stop if $\text{Prob}\{p(\text{ORR}, E) < p(\text{ORR}, H) + 0.15 \mid \text{data}\} > 0.975$, or
- 2) Stop if $\text{Prob}\{p(\text{TOX}, E) > 0.30 \mid \text{data}\} > 0.975$,

where $P(\text{ORR}, E)$ and $P(\text{TOX}, E)$ are the true ORR and toxicity rates for the combination treatment, and $p(\text{ORR}, H)$ is the true ORR rate of the standard treatment. The first rule provides for stopping the study if the data suggest that it is unlikely (i.e., probability $< 2.5\%$) that ORR rate of the combination treatment is greater than the ORR rate of standard treatment by 15.0%. The second condition will stop the study early if excessive therapy-related grade 3/4 toxicity ($>30\%$) is highly probable (i.e., probability $>97.5\%$) for the combination treatment. Monitoring for toxicity and futility will not begin until 5 patients have been evaluated, and cohort size for future evaluations is 5.

The monitoring rule for the toxicity rate, based on these assumptions and monitoring conditions above is found in Table 4. **For example, accrual will cease if 4 or more patients experience toxicities among the first 5 patients.**

Table 4. Stop accrual if the number of drug-related grade 3/4 toxicities is greater than or equal

to indicated (i.e., # patients with toxicities) among the number of patients evaluated								
# patients evaluated	5	10	15	20	25	30	35	40
# patients with toxicities	4-5	6-10	8-15	10-20	12-25	14-30	16-35	Always stop with this many patients

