All patients who received any dose of the study agent will be included in the analysis for efficacy and safety. Demographic/clinical characteristics (including duration of response) and safety data of the patients will be summarized using descriptive statistics such as mean, standard deviation, median and range. For the primary efficacy analysis, we will estimate the ORR for the combination treatment, along with the 95% confidence interval. Patients who drop out of the study before completing all the cycles will be treated as “failures” for the primary analysis. ORR during the study period will also be presented with the 95% confidence interval. The association between ORR and patient’s clinical characteristics will be examined by Wilcoxon’s rank sum test or Fisher’s exact test, as appropriate. Toxicity type, severity and attribution will be summarized for each patient using frequency tables.

The distribution of time-to-event endpoints (DFS and OS) including overall survival and progression free survival will be estimated using the method of Kaplan and Meier. Comparisons of time-to-event endpoints by important subgroups will be made using the log-rank tests. Paired t-tests will be used to determine the immunological and molecular changes in the peripheral blood and bone marrow from baseline to the time of response, and to the time of disease progression. Correlation analysis (such as logistic regression analysis) will be conducted to determine the relationship between induction of hypomethylation / DNA damage and clinical response.

Statistical analysis of biomarker data: Descriptive statistics including plots, mean, median and standard deviations will be used to summarize data. For continuous outcomes, t-test and ANOVA will be used to compare outcome measures across patient characteristics. Dunnett’s and Tukey’s test that properly adjust for multiplicity in multiple tests will be implemented. Pair-wise comparisons will be performed using pre- and post-therapy samples from each patient . The chi-square test or Fisher’s exact test will be used to test the association between two categorical variables such as disease state and performance status. Both univariate and multivariate logistic regressions will be performed to model prognostic factors.

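### Section 11.2 plans multivariable logistic regression on about 6 to 12 responders and names no small-sample estimator; if response is the outcome and ordinary maximum likelihood is used, odds ratios for real effects will tend to be overstated

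*Combined protocol and SAP*

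**What the plan says.** The last paragraph of section 11.2, on biomarker data, ends: "Both univariate and multivariate logistic regressions will be performed to model prognostic factors". It gives no outcome variable, candidate factors, limit on their number, selection rule or estimation method.

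The paragraph before it covers hypomethylation and DNA damage against clinical response: "Correlation analysis (such as logistic regression analysis) will be conducted". Here logistic regression is only an example, and nothing says the model has more than one predictor. Section 1.3 lists this question as exploratory. The same part of 11.2 relates ORR to clinical characteristics by rank-sum or Fisher tests.

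On size, section 11.1 says "Up to 40 patients (including 6 patients treated at the MTD from the lead-in part) will be recruited for the Phase II part" and, for the lead-in, "Up to 24 patients will be accrued into lead-in part of the study". Section 5.2 says the MTD "will be used to treat an additional 34 patients in the phase II portion of the study". On the analysis set, 11.2 says "All patients who received any dose of the study agent will be included in the analysis for efficacy and safety". On response, 11.2 says "Historical data on similar patients shows an ORR of 10-15" per cent and sets a target of 30%. Section 7.2.7 makes all correlative samples optional.

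**The concern.** A logistic model draws its information mainly from the rarer outcome, here the responders. With few responders per covariate, ordinary maximum likelihood pushes coefficients away from zero. If a covariate, or a combination of covariates, divides responders perfectly from non-responders, the estimate is infinite. Neither problem is visible to someone reading a table of odds ratios.

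At stake are the prognostic-factor models and, to a lesser degree, exploratory objective 2. Overstated odds ratios from this trial could be taken up as hypotheses for later studies. The efficacy conclusion of this trial is not at stake.

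**Working it through.** The plan gives no event count, covariate count or precision for these models, so there is no figure of its own to reproduce.

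**1. Responders available** (N × ORR; N from 11.1, rates from 11.2)
- 40 × 0.10 = 4; 40 × 0.15 = 6; 40 × 0.30 = 12.
- Binomial 5th to 95th percentiles: 3 to 10 at 15%; 7 to 17 at 30%.
- Pooling all dosed patients: 24 + 34 = 58; 58 × 0.15 = 8.7 and 58 × 0.30 = 17.4, so about 9 to 17.
- Forty is a ceiling. The stopping rules can end accrual earlier, and counting dropouts as non-responders can lower the responder count.

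**2. Responders per covariate in 40 patients** (6 to 12 divided by the number of covariates)
- 2 covariates: 3 to 6. 4 covariates: 1.5 to 3. 6 covariates: 1 to 2.

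**3. Behaviour of ordinary maximum likelihood**

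The assumptions are N = 40 and one factor with true odds ratio 2 (log odds ratio 0.693). Relative bias is mean estimate / 0.693 − 1.

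*Set A*: 1,500 datasets per scenario; half the covariates normal and half binary with 30% prevalence; the others have no effect. Failure means non-convergence or any coefficient above 10 in absolute value. Mean log odds ratios are from converged fits with 4 and 6 covariates.
- ORR 30%: 0.89 to 0.97, so 0.89/0.693 − 1 = +28% to 0.97/0.693 − 1 = +40%; failure 3% (4 covariates) and 7% (6).
- ORR 15%: 0.94 to 1.04, so +36% to +50%; failure 29% and 41%.

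*Set B*: the factor of interest is continuous; in multivariable models half the covariates are normal and half binary with 30% prevalence; the others have odds ratio 1.5. Separation is detected by linear programming. The responder count is fixed at exactly 6 or 12.

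| Covariates | 6 responders: bias / separation | 12 responders: bias / separation |
|---|---|---|
| 1 | +15% / 0% | +13% / 0% |
| 2 | +22% / 6.5% | +14% / 0.8% |
| 4 | +43% / 13% | +30% / 1.1% |
| 6 | +79% / 21.5% | +42% / 1.9% |

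The Monte Carlo standard error of the relative bias is 0.02 to 0.07. With the responder count left random, separation with 2, 4 and 6 covariates is 12%, 22% and 32% at ORR 15%, and 1.0%, 1.7% and 3.7% at ORR 30%.

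*Set C*: a further set with 2 to 6 covariates.
- ORR 30%: mean 0.81 to 0.98 (+17% to +41%); failure 2 to 8%.
- ORR 15%: mean 0.86 to 1.03 (+24% to +49%); failure 16 to 40%.

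**4. Effects that are truly null.** With all true odds ratios equal to 1 and 4 covariates, the average estimate is 1.00 to 1.02, so there is no average inflation. Separation still occurs in 24% of datasets with 6 responders and 4% with 12.

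**5. One continuous biomarker** (the plain reading of the hypomethylation/DNA-damage analysis)
- All 40 patients sampled: +13% to +15%, no separation (table, first row).
- 30 sampled, 9 responders: +17%, no separation.
- 20 sampled, 3 or 6 responders: +41%, separation at most 1.4%.

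**6. Firth penalised likelihood on the same problems.** Mean log odds ratio 0.69 to 0.72 in set A and 0.66 to 0.72 in set C. In set B, with 1 to 6 covariates in 40 patients, the geometric mean odds ratio is 1.98 to 2.10 against a true 2. In set C it had no failures and a lower root mean squared error in every scenario, including one covariate.

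**The case against.** The strongest objection is that much of this rests on inference. Section 11.2 does not mention maximum likelihood; that is only the default when no estimator is named. It does not say that response is the outcome of the prognostic models, and it gives no covariate count. These points stand, so the conclusion has to be conditional.

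A reader might infer that the odds ratios are bound to be inflated or fail to converge. The documents do not support that. At the 30% target, failure is uncommon (about 1-8% with up to 6 covariates), null effects are not inflated on average, and two covariates with 12 responders give +14% bias and 0.8% separation.

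A reader might also extend the multivariable results to exploratory objective 2. That analysis is not stated to be multivariable. With one predictor and full sampling, the bias is about 0.15 × 0.693 = 0.10. The approximate standard error for a standardised covariate is 1/√(40 × 0.30 × 0.70) = 0.35 at ORR 30% and 1/√(40 × 0.15 × 0.85) = 0.44 at ORR 15%. The bias is therefore small next to the noise and grows mainly if optional samples are missing.

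The number of responders could also be higher. All dosed patients may be pooled, and 11.2 also reports ORR over the whole study period as well as within three months. Pooling 58 patients still leaves about 9 to 17 responders, or roughly 2 to 4 per covariate with four covariates.

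The rank-sum and Fisher tests do suit small counts, but they give no adjusted odds ratios and so do not protect the multivariable model.

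**Conclusion.** The point holds as a minor one. The plan commits to multivariable logistic regression with about 6 to 12 responders in 40 patients and names no small-sample estimator. If response is the outcome and ordinary maximum likelihood is used, then with 2 to 6 covariates:
- log odds ratios for real effects are inflated by roughly 15-40% at ORR 30%, so a true odds ratio of 2 is reported on average as about 2.2 to 2.6 (exp(1.15 × 0.693) to exp(1.40 × 0.693));
- they are inflated by roughly 20-50% at ORR 15%, so a true 2 is reported as about 2.3 to 2.8. One setting, exactly 6 responders and 6 covariates that all have effects, reached +79%;
- separation or non-convergence affects about 1-8% of analyses at ORR 30% and 12-41% at ORR 15%.

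The covariate number, mix and effect sizes are assumptions. The single-predictor hypomethylation/DNA-damage analysis is affected only mildly, about 10-15% on the log odds ratio, unless many samples are missing. No logistic result feeds the primary ORR estimate or the stopping rules.

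**What to change.** In section 11.2:
- fit the logistic models for response by Firth penalised likelihood with profile-likelihood intervals; exact logistic regression is an acceptable alternative;
- state the outcome of the prognostic-factor models, and keep the multivariable model to a short covariate list suited to the number of responders. One or two would fit 6 to 12 responders, though the exact cap is a matter of preference;
- label the results exploratory.

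The cost is a sentence or two and a minor software change. The downside is that fewer covariates can be modelled together. The primary ORR analysis, the stopping rules and the sample size do not change.

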12.0 PROTOCOL ADMINISTRATION

This study will be monitored by the MD Anderson IND Office and a protocol-specific monitoring plan will be followed.

Protocol amendments

Changes to the protocol will be made only when protocol amendments have been signed by the principal investigator and approved by the sponsor and the IRB of the study center.

Archival of data

All patient data (including source data) generated in connection with this study will be kept in the archives of the MDACC for at least 15 years after the study has been completed. All data will be available for inspection by company representatives of the Medical Department and by regulatory authorities.

14.0 APPENDICES

Appendix A: Prioritization List – Priority List

Appendix B: Protocol Checklist

Appendix C: CTCAE version 4.0

Appendix D: Leukemia specific AE recording and reporting guidelines

Appendix E: Lirilumab BMS Investigator Brochure

Appendix F: Vidaza Drug Information

Appendix G: Management algorithms for immuno-oncology drug-related adverse events

Appendix H: Outside Physician Form

Appendix I: DOSING PROCEDURE MANUAL for Lirilumab and Nivolumab Version
2.0
